## 1.0 Objectives / Specific Aims

- Aim 1. Assess the incidence of leukopenia in those randomized to maribavir vs. valganciclovir prophylaxis in adult kidney transplant recipients at high-risk of CMV infection.
  - Hypothesis 1. The incidence of clinically meaningful leukopenia, defined as a WBC count of  $< 3,000$  cells/mm^3 and a reduction in total mycophenolate dose below 1,500 mg/day or valganciclovir dose below 900mg per day (adjusted for renal function), will be significantly lower in the maribavir arm, as compared to the valganciclovir arm.
- Aim 2. Assess the efficacy of maribavir vs. valganciclovir prophylaxis in adult kidney transplant recipients at high-risk of CMV infection.
  - Hypothesis 2. The incidence of CMV infection and disease will be similar between the maribavir arm, as compared to the valganciclovir arm, at 3-, 6-, and 12-months post-transplant.
- Aim 3. Assess the impact of maribavir vs. valganciclovir prophylaxis on healthcare utilization and costs in adult kidney transplant recipients at high-risk of CMV infection.
  - Hypothesis 3. Healthcare utilization will be lower in the maribavir arm, as compared to the valganciclovir arm, at 6- and 12-months post-transplant, driven predominantly by reduced number of telephone calls, televisits, and laboratory monitoring encounters.
- Exploratory Aim 4. Assess the impact of maribavir vs. valganciclovir prophylaxis in adult kidney transplant recipients at high-risk of CMV infection on patient-reported outcomes for quality of life and satisfaction.
- Exploratory Aim 5. Assess any differences in leukopenia, efficacy, healthcare utilization and patient reported outcomes by race and sex in patients randomized to maribavir vs. valganciclovir prophylaxis in adult kidney transplant recipients at high-risk of CMV infection.

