### **Additional Measures**

14. BK Infection (Exploratory Outcome) – defined as BK viremia of at least 2,000 copies/mL. Severe BK infection will be defined at BK viremia of at least 10,000 copies/mL. BK nephropathy will be defined based on the pathology report from the kidney allograft biopsy. The severity and duration of BK infection will be recorded for all patients.
15. Non-CMV, Non-BK Infections (Exploratory Outcome) – defined as any diagnosed and treated infection that leads to hospitalization, and will be sub-classified as bacterial, viral, or fungal etiologies. Opportunistic infections will also be sub-classified for this study as viral, bacterial, or fungal and defined as infections not seen in immunocompetent individuals. The study coordinator capturing clinical event data will review the medical record to determine the timing, severity, treatment regimen and cure time of each infection episode.
16. Healthcare Utilization (Secondary Outcome) – each encounter will be captured during the 12-month study and classified as hospitalizations, ED visits, ambulatory care visits, ambulatory care procedures, radiology encounters, telemedicine visits, telephone calls, and laboratory encounters. Only MUSC encounters will be captured. Data will be analyzed based on utilization type and provider type (Transplant vs. Other). Healthcare charges will be captured from MUSC hospital accounting. Charges will be converted to estimated costs using the Medicare Cost-to-Charge Ratio (CCR) for MUSC. This endpoint will be assessed at 3-, 6-, and 12-months post-transplant.
17. Health-Related Quality of Life (Exploratory Outcome) – the PROMIS QOL will be used to assess health-related quality of life. This questionnaire will be administered to patients at 3-, 6-, and 12-months post-transplant. Results will be compared between study arms.
18. Patient Satisfaction (Exploratory Outcome) – a validated survey provided by will be used to assess patient experience and satisfaction. This instrument will be administered at 3-, 6-, and 12-months post-transplant.

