If necessary, multivariable analysis assessments for Aims 1 and 2 will be conducted using Cox regression time to event models. The primary variable of interest in these models will be treatment (maribavir vs. valganciclovir). If necessary and appropriate given event rates, Cox regression analysis will also be used for survival analyses involving all time to event outcomes, including time to acute rejection, time to graft loss and time to death. Models will be adjusted for key variables known to influence outcomes, including CMV serostatus and rATG induction. To prevent overfitting, no more than one covariate for every 5 events will be included in these models. Given the small sample size and expected event rates, Cox models will likely be overfit if including >2 covariates plus the primary treatment variable. Thus, multivariable modeling will be limited to only include key baseline variables that are known to influence the risk of CMV infection and that significantly differ by treatment arm based on preliminary univariate analyses; this will most likely only include CMV D+/R- serostatus and/or rATG induction. Prior to conducting Cox regression, modeling assumptions will be assessed, including proportionality of hazards across treatment arms and assessing the optimal functional forms of non-dichotomous covariates.

For Aim 3, total hospital charges and healthcare utilization will be modeled using a validated method we have used in previous studies. This will be a two-part statistical models for zero-heavy continuous data. The general format of the suggested model in which we fit a logistic model for the probability of non-zero response and a conditional generalized linear model (GLM) for the mean response given that it is non-zero. We will consider several distributions for the GLM part (eg, log-normal, gamma and Weibull, zero-inflated negative binomial [ZINB]) and the best fitting model will be selected using Bayesian information criterion (BIC). Parameter estimates of percent change in total hospital charge per unit increase in the values of each covariate in the model and their 95% CI will be computed using SAS Proc FMM.

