#### **18.0 Drugs or Devices**

Valganciclovir is considered current gold-standard therapy to prevent CMV infection in transplant recipients. Those randomized to valganciclovir will receive it through usual care processes. The prescription will be filled by the Rutledge Tower Pharmacy or a pharmacy of the patient's choice and it will be billed to the patient's insurance. The patient will be responsible for any copays related to valganciclovir prophylactic therapy. Those randomized to the maribavir arm will receive both the maribavir and acyclovir through the study, dispensed by the MUSC Investigational Drug Services (IDS) at no charge to the patient. The research study coordinator will ensure the patient receives these medications, either by hand delivery to the patient or through mailing the medications to the patient.

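### Aim 3's cost measure gives study-supplied maribavir no evident charge and may capture valganciclovir for only some patients, so it cannot show the cost impact of one drug against the other

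*Combined protocol and SAP*

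**What the plan says.** Section 1.0 states Aim 3 as "Assess the impact of maribavir vs. valganciclovir prophylaxis on healthcare utilization and costs in adult kidney transplant recipients at high-risk of CMV infection". Hypothesis 3 is narrower. It predicts that "Healthcare utilization will be lower in the maribavir arm, as compared to the valganciclovir arm, at 6- and 12-months post-transplant", and it gives no direction for cost.

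Section 4.0, item 16 (a secondary outcome), defines the measure. MUSC encounters only are captured, "classified as hospitalizations, ED visits, ambulatory care visits, ambulatory care procedures, radiology encounters, telemedicine visits, telephone calls, and laboratory encounters". No outpatient pharmacy or drug category is listed. On money it says "Healthcare charges will be captured from MUSC hospital accounting" and "Charges will be converted to estimated costs using the Medicare Cost-to-Charge Ratio (CCR) for MUSC".

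Section 18.0 describes two different supply routes. Maribavir and acyclovir come through the study, "dispensed by the MUSC Investigational Drug Services (IDS) at no charge to the patient". For valganciclovir, "The prescription will be filled by the Rutledge Tower Pharmacy or a pharmacy of the patient's choice", with the bill going to the patient's insurance.

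The Statistical Methods in section 10.0 model total hospital charges and utilization in two parts: a logistic part for any non-zero response, and a GLM for the size of the non-zero responses. They add "We will consider several distributions for the GLM part", naming log-normal, gamma, Weibull and zero-inflated negative binomial (ZINB), with selection by BIC.

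**The concern.** A cost comparison of two drug strategies has to treat the drugs' own cost in a stated way that is the same in both arms. This plan does not. One regimen reaches the patient outside ordinary billing. The other goes through ordinary billing, possibly at a pharmacy whose charges the hospital never sees. No section gives either drug a cost, excludes both, or states whose costs are being counted.

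The consequence is one of interpretation. The plan as written allows a report that maribavir changes costs when 3 or 6 months of maribavir were left unpriced, and when valganciclovir was counted or not according to where each patient filled the prescription.

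**Working it through.** The documents contain no drug price, expected cost or Aim 3 power figure, so there is no stated number to reproduce. What can be checked is the direction of the distortion.

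**Inputs**
- Maribavir and acyclovir: no charge to the patient (section 18.0). I take this to mean no charge in hospital accounting, which is an inference.
- V: the true cost of a valganciclovir course. Not in the documents, so used as the unit.
- r: the cost of maribavir plus acyclovir divided by V. Not in the documents; assumed from 0.25 to 5.
- f: the share of V that reaches MUSC hospital accounting. Not in the documents; assumed from 0 to 1.

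**Formula** (maribavir minus valganciclovir, drug component only)
- True difference = rV − V = V(r − 1)
- Observed difference = 0 − fV = −fV
- Distortion toward maribavir = true − observed = V(r − 1) + fV = V[r − (1 − f)]

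For example, r = 2 and f = 0.5 give 2 − 0.5 = +1.5 V, while r = 0.5 and f = 0 give 0.5 − 1 = −0.5 V.

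| r | f = 0 | f = 0.5 | f = 1 |
|---|---|---|---|
| 0.25 | −0.75 | −0.25 | +0.25 |
| 0.5 | −0.5 | 0 | +0.5 |
| 1 | 0 | +0.5 | +1 |
| 2 | +1 | +1.5 | +2 |
| 5 | +4 | +4.5 | +5 |

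Positive values (in units of V) make maribavir look cheaper than it is; negative values do the reverse.

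**Reading the table**
- The distortion favours maribavir exactly when r > 1 − f.
- If all valganciclovir cost is captured (f = 1), it always favours maribavir, by r.
- If maribavir plus acyclovir costs at least as much as valganciclovir (r ≥ 1), it favours maribavir for every f above 0.
- If no valganciclovir cost is captured (f = 0), the sign depends only on whether r is above or below 1.

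**Volume left unpriced.** Maribavir is taken twice daily, so the omitted supply is about 90 × 2 = 180 doses for a 3-month course or 180 × 2 = 360 doses for a 6-month course. This assumes 90 and 180 days.

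**Model (minor).** The GLM part is fitted only to patients with a non-zero response, so its treatment coefficient compares subsets formed after randomisation. The randomised contrast is the difference in overall means, where each arm's mean is P(Y > 0) × E(Y given Y > 0). ZINB is a count distribution with its own zero component. It does not belong in a BIC comparison with gamma or log-normal densities for positive continuous charges.

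**The case against.** The strongest reply is that the measure already leaves outpatient drugs out of both arms. None of the eight encounter types is pharmacy, only MUSC encounters count, and the modelled variable is called total hospital charges. Nothing says that Rutledge Tower fills enter hospital accounting, and a statement about the patient's bill does not describe accounting entries. On that reading only the label needs correcting. This is a fair reading, and it is why unequal capture is a possibility here and not an established fact. It does not settle the matter, because the plan never states the exclusion and Aim 3 promises a comparison of costs without that limit.

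A reader might infer that the comparison must favour maribavir because its drug is free. The documents do not support this: without prices or the captured share, the distortion can be zero or run the other way. A reader might also infer that the hoped-for savings are counted in full while the drug is not. That fails too. Section 10.0 says outside hospitalizations and ED visits are not accessible, item 16 restricts capture to MUSC encounters, and nothing says telephone calls carry a charge.

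It is also true that Hypothesis 3 concerns utilization, that the outcome is secondary, and that the trial calls itself exploratory. These points limit the scope but do not make the cost result interpretable.

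On the model, nearly every patient will have some charges, given scheduled visits and laboratory tests to month 12. The conditional part therefore matters little for total charges and more for sparse categories such as ED visits. The plan also has univariate tests for continuous outcomes that need no such conditioning. ZINB is a natural choice for the counts, and the sentence may simply be loosely worded. These are reasons to treat the model points as minor.

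**Conclusion.** The point holds in a limited form. The Aim 3 cost result, as planned, cannot be read as the cost impact of maribavir against valganciclovir prophylaxis, because the drugs' own cost is neither valued nor excluded on the same terms in both arms.

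The distortion is V[r − (1 − f)]. Over the assumed ranges it runs from −0.75 to +5 valganciclovir course costs. It tilts toward maribavir if any valganciclovir fills are captured and maribavir costs at least as much. In other cases the direction depends on unknown prices and capture. No amount in currency can be given.

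The conclusion rests on the inference that study-dispensed drug generates no hospital accounting charge. It affects only the cost component of Aim 3. The encounter counts behind Hypothesis 3, the primary leukopenia endpoint and the sample size do not change.

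**What to change.** In item 16 and the Aim 3 methods:

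1. Remove all prophylaxis drug charges (maribavir, acyclovir, valganciclovir) from both arms and name the outcome *MUSC encounter costs excluding prophylaxis drugs*. This sets f = 0 by design, so the part left out is known to be V(r − 1).
2. Add a drug-inclusive analysis that puts this part back. Value each regimen from recorded doses and durations at one common published unit price per drug, over a stated price range. Draw no conclusion that maribavir lowers cost without it.
3. Minor: report the combined two-part mean difference per randomised patient, and use ZINB for encounter counts only.

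Most of the data are already planned. The footnotes to the assessment table in section 10.0 list antiviral drug doses, and items 4 and 5 of section 4.0 record reductions, holds and discontinuations with their duration. Dispensing dates are not listed as collected, so the valuation should rest on doses and durations. Step 1 also requires that prophylaxis drug charges can be identified in the accounting data, which the plan should confirm.

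The cost is a little more analysis work and a possibly less favourable cost result. No visit, treatment or sample-size change is needed.

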## **5.0 Inclusion and Exclusion Criteria/ Study Population**

### **Inclusion Criteria**

1. Kidney transplant recipient at study institution
2. ≤7 days of transplant
3. Received at least one dose of rATG induction or patient is D+/R- CMV serostatus
4. Persons with impaired decision making

### **Exclusion Criteria**

1. Age <18 years at time of transplant
2. Recipient of pancreas, liver, heart, lung transplant

### 3. Recipient of investigational, non-FDA approved medication

#### 6.0 Number of Subjects

70 patients will be randomized 1:1 (35 in each arm) in blocks of 10. Once a patient is randomized and receives at least one dose of CMV prophylaxis medication they will be included in the study in an intent-to-treat manner. Those that are lost to follow-up, withdraw, or are taken off study drug will not be replaced.

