### 3.0 Intervention

Patients will be randomized to receive either maribavir 400mg PO BID or valganciclovir 900mg daily (standard of care dose, adjusted for renal function) for CMV prophylaxis for 3 to 6 months post-transplant. Those that are CMV serostatus D+/R- will receive 6 months of antiviral therapy; all others will receive 3-months of therapy. The current gold-standard therapy is valganciclovir for 3- to 6-months of therapy. Those randomized to maribavir will also receive 1-month of acyclovir 400mg PO BID for HSV prophylaxis (standard of care dose). Beyond these interventions, all follow-up care and laboratory monitoring will be conducted as per usual care protocols. All immunosuppression will be given and dosed as per usual care protocols. There will be no additional visits or laboratory measurements as part of this study.

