#### 7.0 Setting

There will be one study site, the Medical University of South Carolina Kidney Transplant Center. The MUSC IRB will review and approve the study and protocol. Patients will be screened, approached, consented, and randomized prior to discharge from the hospital for their kidney transplant event on 6E or during a routine clinic appointment (9th floor RT) as long as it is within 7 days of transplant.

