#### 8.0 Recruitment Methods

Each weekday, the study coordinator will review the kidney transplant roster to determine new patients that received a transplant within the past 24 to 72 hours. The coordinator will screen each patient to determine if they meet inclusion and exclusion criteria and review with the study team prior to approaching for consent.

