#### 10.0 Study Design / Methods

This will be a 12-month, single-center, open-label, randomized controlled clinical trial enrolling 70 total patients (35 in each arm). Given the limited sample size and single center design, this is a small, exploratory trial with limited power to detect significant differences between treatment arms for rates of CMV infection and other clinical endpoints (acute rejection, graft loss, death). The study is powered to detect clinically meaningful and statistically significant differences in the incidence of leukopenia accompanied by a reduce in total mycophenolate dose or valganciclovir dose (see power/sample size section). Patients will be randomly assigned to receive valganciclovir

900mg PO daily (this is considered standard usual care, adjusted for renal function) for 3-6 months post-transplant (based on CMV D/R serostatus as detailed below) or maribavir 400mg PO BID for 3-6 months post-transplant (based on CMV D/R serostatus as detailed below) + acyclovir 400mg PO BID for 1-month post-transplant (investigation arm, the addition of acyclovir to maribavir is considered standard usual care for HSV prophylaxis). Patients that are D+/R- will receive 6 months of prophylaxis, while all other CMV serostatuses will receive 3 months of prophylactic therapy (per MUSC usual care CMV protocol). All other medications, including immunosuppression and additional anti-infective prophylaxis, will be per standard usual care. All follow-up laboratory assessments and clinic visits will occur as per usual care as well. The only additional procedure specific to this study is that patients will be self-administered two surveys at 3, 6, and 12-months post-transplant, which can be completed online during a routine clinic visit or at home. There will be no visits conducted solely for this research study.

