### **Power/Sample Size**

This study is adequately powered to detect a clinically meaningful and statistically significant difference in the incidence of clinically significant leukopenia in those randomized to maribavir vs. valganciclovir under most incident rate scenarios. For this study, clinically significant leukopenia is defined as a WBC count of <3,000 AND a reduction in the dose of mycophenolate or valganciclovir dose. Based on a retrospective analysis of internal data, the expected incidence of clinically significant leukopenia in the valganciclovir arm is between 33 and 35%. To support this incident rate, we conducted a retrospective analysis of our internal data to fully assess the incidence of clinically significant leukopenia. In this analysis, we included 446 adult kidney transplant recipients transplanted at MUSC between 2007 and 2015. We chose this time period as we had comprehensive data on induction, WBC counts, and MMF dosing to allow for assessment of the incidence of clinically significant leukopenia. Of these patients, 127 (28%) received rATG induction. The incidence of WBC <3K with and without MMF dose reduction is detailed in the table below, which was assessed within 1 year of transplant. This data matches our expected incidence of leukopenia in the VGC arm of 35%. This is because patients in the proposed study will be receiving rATG or be CMV D+/R- and receive 6-months of VCG/maribavir and be at higher risk of leukopenia.

[figure not shown]
Induction Agent	N	WBC <3K	WBC <3K and MMF Dose Reduction
Basiliximab	319	36.7%	21.3%
rATG	127	56.7%	34.6%

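### Randomisation is not stratified by D+/R- serostatus and adjustment for it is conditional; separately, the single disclosed block size of 10 makes about 1 in 6 allocations deducible

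*Combined protocol and SAP*

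**What the plan says.** All references are to the combined protocol and SAP.

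- **Allocation.** Section 6.0: "70 patients will be randomized 1:1 (35 in each arm) in blocks of 10". No section names a stratification factor, a second block size, how the sequence is generated, how it is concealed, or who holds the list.
- **Setting.** Section 10.0: "This will be a 12-month, single-center, open-label, randomized controlled clinical trial enrolling 70 total patients". Section 7.0: "There will be one study site, the Medical University of South Carolina Kidney Transplant Center".
- **Serostatus and exposure.** Section 3.0: "Those that are CMV serostatus D+/R- will receive 6 months of antiviral therapy; all others will receive 3-months of therapy". The assessment table in section 10.0 places donor and recipient CMV serology before transplant.
- **Eligibility.** Section 5.0 admits a patient who "Received at least one dose of rATG induction or patient is D+/R- CMV serostatus", so two risk groups are mixed by design.
- **Link to the primary outcome.** To support the expected valganciclovir rate, Power/Sample Size says that patients will be receiving rATG or "be CMV D+/R- and receive 6-months of VCG/maribavir and be at higher risk of leukopenia".
- **Who recruits.** Section 8.0: "The coordinator will screen each patient to determine if they meet inclusion and exclusion criteria and review with the study team prior to approaching". Section 18.0 has the research study coordinator see that maribavir patients get their drug, by hand or by mail.
- **Analysis.** Statistical Methods (section 10.0) compares leukopenia incidence by chi-square or Fisher's exact test. Cox models follow only where judged necessary. One sentence says that they adjust for serostatus and rATG; a later one keeps only baseline variables that differ significantly by arm.

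**The concern.** Serostatus is fixed and known when a patient is randomised, and it doubles the planned duration of study drug. Simple blocking balances total numbers but not the D+/R- share. If one arm happens to receive more D+/R- patients, it has longer planned exposure and, on the plan's own reasoning, a different leukopenia risk. CMV infection could be affected too, since the Background lists D+/R- among the high-risk groups. The analysis offers no dependable correction, because a significance test decides whether serostatus enters the model.

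The block size is a different matter. With one size printed in the protocol and all treatments visible at one site, a person who keeps count can work out the end of each block. Consent may be sought up to day 7, which leaves some room over whom to approach and when. Selection on that knowledge would be a true bias that no analysis could reliably remove. The primary endpoint also requires a dose reduction decided by clinicians who know the treatment.

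**Working it through.** **1. The plan's own figures.** 70 / 10 = 7 blocks and 7 × 5 = 35 per arm, as stated. The stated 32 per arm also reproduces: for 33% versus 6%, a likelihood-ratio chi-square calculation gives 64 in total with power 0.809, which is the value in the plan's table. Nothing below changes the sample size.

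**2. Chance imbalance in D+/R-.** The documents do not give the D+/R- share f, so it is taken as 20–40% (assumption). With 35 per arm, each arm's D+/R- count is Binomial(35, f). Since 5/35 = 14.3% and 6/35 = 17.1%, a difference of at least 15 points means at least 6 patients; since 7/35 = 20%, at least 20 points means at least 7. Summing the exact joint probabilities:

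| Assumed f | SD of difference, √(2f(1−f)/35) | P(≥15 points) | P(≥20 points) |
|---|---|---|---|
| 0.20 | 0.096 | 10% | 5% |
| 0.30 | 0.110 | 15% | 9% |
| 0.40 | 0.117 | 18% | 11% |

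**3. Would the covariate rule catch it?** Take 14 of 35 versus 7 of 35 (40% versus 20%):

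- chi-square = 70 × (14×28 − 21×7)² / (21 × 49 × 35 × 35) = 70 × 245² / 1,260,525 = 3.33, so p = 0.068;
- Fisher's exact p = 0.117.

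The plan gives no threshold for this screen. At the usual 0.05, a 20-point imbalance in serostatus passes without adjustment.

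**4. What an imbalance could do to the result.** The documents give no leukopenia rate by serostatus. If D+/R- shifts the risk by 10–20 points (assumption), an imbalance of 15–20 points moves the arm difference by 0.15 × 10 = 1.5 to 0.20 × 20 = 4 points. The planned difference is 33 − 6 = 27 to 35 − 5 = 30 points.

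**5. Deducible allocations.** For a block with m = 5 per arm:

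- expected number known with certainty at the end of the block = 2m/(m+1) = 10/6 = 1.67, that is 16.7%, and 7 × 1.67 = 11.7 of 70;
- expected correct best guesses = m + (2^(2m)/C(2m,m) − 1)/2 = 5 + (1024/252 − 1)/2 = 6.53 of 10, that is 65.3%, against 50% by chance.

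**6. Other block sizes.**

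| Scheme | Known with certainty | Best guess correct |
|---|---|---|
| Fixed 10 (as planned) | 16.7% | 65.3% |
| Fixed 6 | 25.0% | 68.3% |
| Fixed 4 | 33.3% | 70.8% |
| Varying 4/6, stratified, sizes undisclosed | largely removed | 68.7% (simulated, f = 20–30%) |

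Varying undisclosed sizes take away certainty. They do not lower the success of simply guessing the arm that is behind.

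**The case against.** The strongest reply has five parts.

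- **Serostatus is partly handled.** Statistical Methods names it for adjustment. That is true, but the adjustment is optional and screened by significance, and step 3 shows that the screen can miss a 20-point difference.
- **The effect on the primary result is modest.** This stands. A shift of 1.5–4 points is small beside a planned difference of 27–30 points.
- **Serostatus may not be the best stratum.** The only leukopenia rates that the plan gives by risk group are for induction: 34.6% with rATG and 21.3% with basiliximab. Every patient who is not D+/R- must have had rATG, whereas D+/R- patients need not have, so longer exposure and milder induction could partly offset each other. This tempers the expected gain. D+/R- remains the factor that sets treatment duration.
- **Small blocks are no cure.** This stands: best-guess accuracy rises from about 65% to 69% with blocks of 4 and 6. The remedy must rest on concealment and undisclosed sizes.
- **Stratified inference will be sparse.** Only 0.05 × 35 = 1.75 to 0.06 × 35 = 2.1 maribavir events are expected, so large-sample Mantel-Haenszel inference alone would be fragile. This stands and shapes the fix.

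A reader might also infer that recruitment is being steered, or that concealment is absent. The documents show neither. They are silent on concealment, they do not say whether the screening coordinator is also the one who delivers maribavir, and section 8.0 describes routine weekday screening of transplants from the previous 24 to 72 hours.

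**Conclusion.** Both points hold, as separate and inexpensive improvements.

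1. Allocation ignores a known variable that sets treatment duration, and the analysis adjusts for it only conditionally. For an assumed D+/R- share of 20–40%, the chance of an arm difference is 10–18% for at least 15 points and 5–11% for at least 20 points.
2. With one disclosed block size, about 12 of 70 allocations are deducible by someone who tracks the blocks. The plan describes no concealment.

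Three stronger readings might be inferred and are not supported. The allocations are not predictable as a whole: about 58 of 70 cannot be known with certainty. Missing stratification does not cause predictability, and stratifying with the same disclosed block would not cure it. Chance imbalance does not bias the randomised comparison on average; it costs precision and can distort the one result that this trial yields. Nor do the documents rank D+/R- as the main CMV risk factor: the Background names it alongside rATG without ordering them.

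The conclusion rests on the assumed D+/R- share and on reading the single stated block size as fixed.

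**What to change.** - **Stratify** randomisation by D+/R- (yes/no). If enrolment has begun, apply this to the remaining allocations.
- **Conceal.** Allocate centrally, for example through a REDCap randomisation module, since REDCap is already the trial's data system. Use randomly varying block sizes, keep them out of any document that recruiting staff see, and state who generates and holds the list. Record that this removes certain knowledge but does not reduce best-guess accuracy.
- **Adjust** the primary leukopenia comparison for the D+/R- stratum unconditionally: a Mantel-Haenszel risk difference with an exact stratified test, to suit the sparse maribavir events. This replaces the rule in Statistical Methods that lets serostatus in only if it differs significantly by arm.

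The cost is a new allocation list and a few protocol sentences. With blocks of at most 6, the arms can differ by at most 3 patients in either stratum. The total difference is then at most 6 (38 versus 32), and the final arms will more often be close to 35/35. The sample size stays 70.
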